6.9 EFFICACY

6.9.1 PRIMARY AND SECONDARY EFFICACY ENDPOINTS

- Change in Panic Disorder Symptom Severity Scale (PDSS)- primary efficacy endpoint.
- Number of panic attacks
- Change in Clinical Global Impression-Severity Scale (CGI-S)
- Change in Quality-of-Life Enjoyment and Satisfaction Questionnaire Short Form (Q-LES-Q-SF)
- Change in Leibowitz Social Anxiety Scale (LSAS)
- Change in Assessment of Overall Sleep Quality -- Question #6 from the Pittsburgh Sleep Quality Index

6.9.2 EXPLORATORY ENDPOINTS

- Change in Toronto Alexithymia Scale (TAS-20)
- Change in Hamilton Anxiety Rating Scale (HAM-A)
- Change in Montgomery-Asberg Depression Rating Scale (MADRS) only for patients with a medical history of depression
- Change in CogScreen Symbol Digit Coding test (SDC)
- Change in Conners' Adult ADHD Rating Scale (CAARS) only for patients with a medical history of ADHD
- Change in the PTSD Checklist for DSM-5 only for patients with a medical history of PTSD
- Change in Short Form McGill Pain Questionnaire (SF-MPQ) only for patients with a medical history of chronic pain
- Change in Migraine Disability Assessment Questionnaire (MIDAS) only for patients with a medical history of migraine

6.10 SAFETY

6.10.1 SAFETY ENDPOINTS

Incidence of Treatment Emergent Adverse Events (TEAEs), clinically significant changes in clinical laboratory values, changes in electrocardiogram (ECG), and Columbia Suicide Severity Rating Scale (C-SSRS), and orthostatic vital signs.

6.10.2 ADVERSE EVENTS

All AEs should be captured on the eCRF from Visit 2/Week 0 through the Safety Follow-up visit. Adverse events considered at least possibly related to study treatment should be followed until resolution, return to baseline, or deemed chronic or stable.

All serious adverse events (SAEs) will be immediately reported to the Sponsor from the time of Visit 2/Week 0 (dosing) through the Safety Follow-up/End of Study Visit.

6.10.3 LABORATORY ASSESSMENTS

The following laboratory parameters will be measured at the time points specified in the Schedule of Assessments and will be analyzed locally:

- Pregnancy test should be administered for women of child-bearing potential (WOCBP) within 7 days prior to Week 0 and then at each subsequent study visit.
- Comprehensive Metabolic Panel (CMP): albumin, blood urea nitrogen, calcium, carbon dioxide, chloride, creatinine, creatinine phosphokinase, glucose, potassium, sodium, total bilirubin, total protein, alanine aminotransferase (ALT), alkaline phosphatase (ALP), aspartate aminotransferase (AST)
- Complete Blood Count (CBC): white blood cell count, red blood cell count, hematocrit, hemoglobin, mean corpuscular volume (MCV), mean corpuscular hemoglobin (MCH), mean corpuscular hemoglobin concentration (MCHC), red cell distribution (RDW), platelet count, mean platelet volume (MPV), Vitamin B12
- Urinalysis: microscopic examination, specific gravity, pH, protein, glucose, ketones, blood and urobilinogen

6.11 STOPPING CRITERIA

Table 2: Subject Specific Stopping Criteria

Cardiac Disorders	
Hypotension	
 • SBP <90 mmHg and DBP <60 mmHg for three consecutive readings 10 minutes apart
Orthostatic Hypotension	
 • Decline of >20mm Hg in systolic or >10 mm Hg in diastolic blood pressure after 3 minutes of standing.
New-onset 2nd or 3rd degree AV block	
 • Grade 1 or higher per CTCAE V5.0*
Sick sinus syndrome	
 • Grade 1 or higher per CTCAE V5.0
Atrial flutter	
 • Grade 1 or higher per CTCAE V5.0
Atrial fibrillation	
 • Grade 1 or higher per CTCAE V5.0
New-onset bradycardia	
 • Resting heart rate below 50
New-onset tachycardia	
 • Resting heart rate above 120
Onset of angina pectoris	
 • Grade 1 or higher per CTCAE V5.0
Congestive heart failure	
 • Grade 1 or higher per CTCAE V5.0
Pulmonary edema	
 • Grade 1 or higher per CTCAE V5.0
Peripheral edema	
 • Grade 1 or higher per CTCAE V5.0
Pulmonary edema	
 • Grade 2 or higher per CTCAE V5.0

General Disorders	
Urticaria	
 Grade 2 or higher per CTCAE V5.0
Hyperkalemia	
 Potassium values that are 2X the ULN for the local lab normal reference ranges. Values may be repeated and confirmed.
Gout exacerbation	
 Hyperuricemia Grade 1 or higher per CTCAE V5.0 Values may be repeated and confirmed.
Impaired hepatic function	
 ALT, AST, ALP values that are twice the upper or lower limit of local lab normal reference range. Values may be repeated and confirmed.
Impaired renal function	
 Doubling in creatinine value. Values may be repeated and confirmed.
Thrombocytopenia	
 Platelet count values below 150,000/mL Values may be repeated and confirmed.

*Common Terminology Criteria for Adverse Events (CTCAE) V5 dated 27Nov2017

7 STATISTICAL ANALYSES

7.1 GENERAL CONSIDERATIONS

All analysis dataset preparations and statistical analyses will be performed using SAS® version 9.4 or higher. Study data will be provided in listings and sorted by patient number, study period, and assessment time. The study results will be displayed using descriptive summary tables and inferential analyses completed as described below. Summaries will be displayed by treatment group for all tables. For measurements that have multiple intermediate visits, results for observed data will be summarized for each time point.

Standard numeric descriptive statistics include number of patients or records observed, mean, standard deviation, median, minimum, and maximum values. Standard categorical descriptive statistics include the count and percentages of patients.

7.2 STUDY DAY AND VISIT WINDOW DEFINITIONS

The baseline assessment from which to include baseline in the analysis model and for the calculation of change scores for all efficacy endpoints is defined as last assessment prior to the first dose of study treatment.

Data obtained during unscheduled and early discontinuation visits will be allocated to the scheduled visit corresponding to the visit window in which they fall in as specified in Table 3.

Data will be analyzed based on the nominal visits and nominal time points. If the data from the nominal visit or time point is missing, data from unscheduled visits or an early discontinuation visit for the same nominal visit or time point will be used.

If multiple visits among unscheduled or early termination assessments fall in the same visit window or time point, the non-missing assessment closest to target time point will be selected for analysis. If multiple values are the same number of days away from the target study day, then the latter value will be used. In the unlikely event an unscheduled or early discontinuation visit, associated with a particular visit window, falls either prior to the actual previous nominal visit date or after the subsequent nominal visit date, it will not be used.

The first date on which subject receives study treatment is defined as Study Day 1. Study days for other visits will be calculated as follows:

Before Study Day 1 visit: Study Day = date of assessment – date of Study Day 1.

On or after Study Day 1 visit: Study Day = date of assessment – date of Study Day 1 + 1.

The target study days of Visits are summarized below.

Table 3: Time Windows for Assessments (unscheduled and early discontinuation visits)

Scheduled Visit Number	Nominal Visit (label)	Time Window (day)	Target Time Point (day)
1	Screening	≤ -1	≤ -1
2	Visit 2 (Baseline/Day 1)	1	1
3	Visit 3 (Week 2)	2 to 21	14
4	Visit 4 (Week 4)	22 to 42	28
5	Visit 5 (Week 8)	43 to 70	56
6	Visit 6 (Week 12)	71 to < Safety Follow-up Visit	84

7.3 ANALYSIS POPULATIONS

Analyses will be performed comparing treatment groups for each of the following populations:

- All Patients – all patients who sign informed consent and are assigned a unique patient identification number.
- Intent-to-Treat (ITT) – all patients who are successfully randomized to either the HB-1 or control treatment groups. This will be the primary population used for efficacy analyses. Patients will be analyzed according to randomized treatment group.
- Safety Population – patients who are randomized and receive at least one dose of study drug. This will be the primary population used to summarize all safety data. Safety summaries will be based on the treatment that patients receive.

7.4 SAMPLE SIZE DETERMINATION

Assuming a standard deviation of 4.5 for the PDSS, 80 patients will provide more than 95% power to detect a difference in the mean change (from baseline) in the PDSS score of 3.75 at an

alpha-level of 0.05 at 12 weeks. This corresponds to a 50% reduction in mean PDSS scores on HB-1 and a 25% reduction in mean PDSS scores on placebo, assuming baseline mean PDSS scores of 15 for both groups.

In addition, with respect to adverse events, the study has approximately 95% power to detect at least one patient with an event that occurs in 7.2% of patients in either treatment group.

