9. STATISTICAL METHODS

9.1. General Considerations

This is a multicenter, randomized, double-blind placebo-controlled trial. All patients will be randomized in a 1:1 ratio to receive an oral dose of HB-1 or matching placebo once a day. Study data will be provided in listings and sorted by patient number, study period, and assessment time. The study results will be displayed using descriptive summary tables and inferential analyses completed as described below. Summaries will be displayed by treatment group for all tables. For measurements that have multiple intermediate visits, results for observed data will be summarized for each time point.

Standard numeric descriptive statistics include number of patients or records observed (N), mean, standard deviation (std), median, minimum (min), and maximum (max) values. Standard categorical descriptive statistics include the count and percentages of patients with a level of the variable summarized. Hypothesis tests will assess the null hypothesis that there is no difference between HB-1 and placebo treatment arms. Testing will be done at the 0.05 alpha-level. Any confidence intervals provided will be at 95% confidence.

All summaries, statistical analyses, and individual patient data listings described below will be completed using Version 9.4 or later of the SAS Statistical Analysis System (SAS Institute, Inc. Cary, NC).

Additional details regarding estimands, including handling of intercurrent events will be provided in a separate statistical analysis plan (SAP) to be finalized prior to completion of the study and unblinding.

Determination of Sample Size

A sample size of 80 patients is planned for the study to be randomized in a 1:1 ratio of active to control.

Assuming a standard deviation of 4.5 in the PDSS, 80 patients will provide for in excess of 95% power to detect a difference in the mean change (from baseline) in the PDSS score of 3.75 at an alpha-level of 0.05 at 12 weeks. This corresponds to a 50% reduction in mean PDSS scores on HB-1 and a 25% reduction in mean PDSS scores on placebo, assuming baseline mean PDSS scores of 15 for both groups.

In addition, with respect to adverse events, the study has approximately 95% power to detect at least one patient with an event that occurs in 7.2% of patients in either treatment group.

Analysis Populations

Analyses will be performed comparing treatment groups for each of the following populations:

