All Patients – all patients who sign informed consent and are assigned a unique patient identification number.

Intent-to-Treat (ITT) – all patients who are successfully randomized to either the HB-1 or control treatment groups. This will be the primary population used for efficacy analyses. Patients will be analyzed according to randomized treatment group.

Safety Population – patients who are randomized and receive at least one dose of study drug. This will be the primary population used to summarize all safety data. Safety summaries will be based on the treatment that patients actually receive.

Handling of Missing Data

Data may be missing either because an assessment is not completed or if patients have withdrawn consent from further participation in the study. Additional details for handling missing data will be dependent on the extent of missing data and will be specified in the SAP.

Adjustments of Multiplicity

To control for multiplicity of select analyses, a hierarchical approach will be used to test the following endpoints in order, each at the 0.05 alpha-level. These endpoints are 1) PDSS (primary efficacy endpoint), 2) mean number of panic attacks, 3) CGI-S. Irrespective, of the significance of these specific measures, planning for future studies will be based on the totality of safety and efficacy data and nominal p-values will be reported for all inferential tests.

Interim Analyses

Interim analyses are not planned for this study.

Patient Disposition

Patient disposition will be summarized for the All Patients population and summarized by treatment group and overall for all patients. The number and percentage of patients who are screened, screen-failed, randomized, and completed the treatment period, follow-up period, or discontinued the study (including reasons for discontinuation) will be presented.

Demographics and Baseline Characteristics

Demographics information will be summarized using descriptive statistics. For gender, race, and ethnicity the summarization of those categorical values will be performed using percentages and frequency. Age, height, weight, and BMI will be summarized using descriptive statistics as total number of patient observed (n), mean, median, minimum, and maximum. Listings and summaries of demographics, baseline characteristics, and medical history, will be summarized by treatment group for the Safety population.

Extent of Exposure to Study Medications and Treatment Compliance

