7.8 MULTIPLICITY ADJUSTMENTS

To control for multiplicity of select analyses, Hochberg's procedure will be used to test the protocol designated primary endpoint (PDSS) as well as the key secondary endpoint CGI-S,

which are not expected to be negatively correlated. Accordingly, if the largest p-value among these two endpoints (at the primary time point) does not exceed 0.05, then both endpoints will be considered statistically significant. If the largest p-value exceeds 0.05 and the smallest p-value does not exceed 0.025, then the endpoint with the smaller p-values will be considered statistically significant. This provides control of the familywise error rate at $\alpha = 0.05$ such that either of the 2 endpoints statistically significant according to the above procedure will constitute a successful efficacy outcome for the trial.

Irrespective of the significance of these specific measures, planning for future studies will be based on the totality of safety and efficacy data and nominal p-values will be reported for all inferential tests.

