7.11 EFFICACY AND EXPLORATORY ANALYSES

7.11.1 PRIMARY AND SECONDARY EFFICACY ENDPOINTS

- Panic Disorder Symptom Severity Scale (PDSS)- primary efficacy endpoint
- Number of panic attacks – key secondary endpoint
- Clinical Global Impression-Severity Scale (CGI-S) – key secondary endpoint
- Quality-of-Life Enjoyment and Satisfaction Questionnaire Short Form (Q-LES-Q-SF)
- Leibowitz Social Anxiety Scale (LSAS)
- Assessment of Overall Sleep Quality -- Question #6 from the Pittsburgh Sleep Quality Index

The primary analysis of efficacy will be performed using the ITT population. The change from baseline to in PDSS will be compared between HB-1 and placebo using Mixed Model Repeated Measures (MMRM) model using SAS mixed procedure with repeated measures. The model will include the fixed effect of treatment, visit, the treatment-by-visit interaction, baseline, baseline-by-visit. The outcome will be the change from baseline to each on-treatment time point. All protocol-scheduled time points will be included in the model. The model will use the unstructured or Toeplitz (whichever has a better fit by AICC value) within-subject variance-covariance matrix. The denominator degrees of freedom will be according to the method of Kenward-Roger. The estimated least square (LS) means and their standard errors as well as the estimated treatment effect (differences between treatments at each time point) will be summarized by treatment. In addition, the 95% CIs of the LS means and the difference between treatments, p-values for treatment comparisons will be provided. The primary analysis

timepoint will be at 12 weeks. Secondary endpoints will be analyzed similarly. For endpoints without a baseline measurement, baseline and the visit-by-baseline interaction will be omitted from the model.

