8 CHANGES FROM PROTOCOL

Hochberg's procedure is now used to control the familywise error rate for the primary endpoint and the key secondary endpoints of the number of panic attacks and the CGI-S. In addition, subgroup analyses of efficacy endpoints are added for participants who are not receiving concomitant benzodiazepines at baseline.

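### SAP 7.4 keeps the protocol's power claim of above 95% for PDSS, but the Hochberg rule in SAP 7.8 no longer assures it

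*SAP*

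**What the plan says.** Protocol 9.1 (Determination of Sample Size) says that "80 patients will provide for in excess of 95% power to detect a difference in the mean change" of 3.75 PDSS points, with an SD of 4.5 and alpha 0.05. Its multiplicity paragraph fits that claim: "a hierarchical approach will be used to test the following endpoints in order, each at the 0.05 alpha-level", with PDSS first, then number of panic attacks, then CGI-S. PDSS therefore had the whole 0.05.

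SAP 7.4 repeats the claim with the same SD, difference, number of patients and alpha: "Assuming a standard deviation of 4.5 for the PDSS, 80 patients will provide more than 95% power".

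SAP 7.8 changes the decision rule to Hochberg over PDSS and CGI-S. The second step begins "If the largest p-value exceeds 0.05 and the smallest p-value does not exceed 0.025"; in that case only the endpoint with the smaller p-value is declared significant. Trial success is also redefined: "either of the 2 endpoints statistically significant according to the above procedure will constitute a successful efficacy outcome for the trial".

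SAP Section 8 describes the same change but applies Hochberg to "the primary endpoint and the key secondary endpoints of the number of panic attacks and the CGI-S", which makes three endpoints. SAP 7.11.1 has the matching label "Number of panic attacks – key secondary endpoint".

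**The concern.** The decision rule changed between protocol and SAP, but the power statement did not. Under the protocol, a PDSS p-value of 0.04 is significant whatever the other endpoints show. Under SAP 7.8 the same p-value is significant only if CGI-S is also at or below 0.05. Power computed for an unsplit 0.05 test is therefore the most that Hochberg can deliver for PDSS, not what it assures.

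A reader of 7.4 takes the chance of missing the planned PDSS effect to be under 5%. Anyone interpreting a non-significant PDSS result would rely on that figure. How far it is off depends on whether the family has two endpoints (7.8) or three (Section 8), and the SAP contradicts itself on that.

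**Working it through.** **Inputs.** Difference 3.75 and SD 4.5 (SAP 7.4); 80 patients randomized 1:1, so 40 per arm (SAP 6.2); two-sided testing (protocol synopsis, Statistical Methodology). Two assumptions are needed because 7.4 is silent: 4.5 is the SD of the change score, and all 80 patients are evaluable at Week 12.

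**The plan's own figure.** Noncentrality = 3.75 / (4.5 × √(2/40)) = 3.75 / 1.0062 = 3.727, with 78 degrees of freedom. At two-sided 0.05 the critical t is 1.991 and power is 95.7%. The normal approximation gives Φ(3.727 − 1.960) = 96.1%. The claim of above 95% reproduces.

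**Bounds under Hochberg.** With k endpoints, PDSS is always rejected if its p-value is at or below 0.05/k and never rejected if it is above 0.05. PDSS power therefore lies between the power at 0.05/k and the power at 0.05, whatever the effects on the other endpoints and the correlations.

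| PDSS threshold | Critical t | Power (t) | Power (normal) | Chance of missing the effect (t) |
|---|---|---|---|---|
| 0.05 | 1.991 | 95.7% | 96.1% | 4.3% |
| 0.025 (two endpoints, lowest) | 2.286 | 92.3% | 93.1% | 7.7% |
| 0.0167 (three endpoints, lowest) | 2.447 | 89.7% | 90.9% | 10.3% |

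The range is 92.3% to 95.7% under 7.8, and 89.7% to 95.7% under Section 8.

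**Where in the range.** The SAP gives no planned effect for CGI-S or panic attacks, so this was simulated (400,000 trials, normal outcomes, 40 per arm, PDSS effect 3.75/4.5 = 0.83 SD). The other effects and the correlation of 0.5 are assumptions; with three endpoints, both secondaries have the same effect.

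| Effect on the other endpoint(s), SD | 0.3 | 0.5 | 0.65 | 0.83 |
|---|---|---|---|---|
| PDSS power, two endpoints | 92.5% | 93.2% | 94.3% | 95.3% |
| PDSS power, three endpoints | 89.9% | 91.1% | 92.7% | 94.7% |

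With two endpoints, PDSS power passes 95% only when the CGI-S effect is about 0.73 to 0.82 SD (correlation 0.3 to 0.7), close to the PDSS effect itself. With three endpoints and all effects at 0.83 SD, it is 95.0%, 94.7% and 94.4% at correlations 0.3, 0.5 and 0.7.

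**Baseline adjustment.** The planned MMRM adjusts for baseline: "The model will include the fixed effect of treatment, visit, the treatment-by-visit interaction, baseline, baseline-by-visit". If 4.5 is the SD of change before adjustment and r is the correlation of change with baseline, the residual SD is about 4.5 × √(1 − r²). Power then returns to 95% at r of about 0.33 for the 0.025 threshold and about 0.42 for 0.0167. At r = 0.2 it is 93.3% and 91.0%; at r = 0.5 it is 97.7% and 96.6%.

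**Missing data.** With 38 evaluable per arm (assumed, completers only), power at 0.05 is already 94.8%. Follow-up after treatment discontinuation and the MMRM would recover part of that loss.

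**The case against.** The strongest reply has three parts.

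First, 7.4 names its alpha of 0.05, and at that level it is true. This stands: the arithmetic is not wrong. But 7.8 no longer gives PDSS an unconditional 0.05, and neither 7.4 nor 7.6 says so.

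Second, the shortfall is computed for an unadjusted t-test, which is not the planned analysis. Suppose the baseline and Week 12 SDs are equal and the within-patient correlation is 0.5. An SD of change of 4.5 then implies a change–baseline correlation of magnitude 0.5, and adjusted power exceeds 95% even at 0.0167. This stands as a possibility, and the ranges above are not bounds for the MMRM. However, equal SDs are hard to square with entry restricted to PDSS 13 or above and an assumed baseline mean of 15, which suggests a compressed baseline distribution. The SAP also does not say whether 4.5 is before or after adjustment, so it cannot count on the gain.

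Third, success under 7.8 is significance on either endpoint, and that probability can be higher: 98.1% with two endpoints, both effects 0.83 SD and correlation 0.5. This is correct, but 7.4 speaks of detecting the PDSS difference, not of trial success.

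It is also fair that the 89.7% figure applies only if Section 8 governs rather than 7.8, and that the gap under 7.8 is small when CGI-S has a sizeable effect.

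**Conclusion.** The concern holds. The SAP changed the PDSS decision rule and kept a power statement that belongs to the old one. On the stated simple basis, the lower ends of the two ranges are 2.7 points (two endpoints) and 5.3 points (three endpoints) below 95%. The low end applies when the other endpoints show little effect; the high end when they too are significant.

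The result rests on 4.5 being the SD of change, no baseline adjustment and complete Week 12 data. Baseline adjustment would raise power and missing data would lower it. What is affected is the stated planning power. The protocol's own sample-size text has no alpha problem, because its hierarchy tests PDSS first at 0.05.

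**What to change.** 1. Reconcile the Hochberg family: two endpoints in SAP 7.8 or three in Section 8.
2. Restate the PDSS power in 7.4 for the rule that governs: about 92% to 96% with two endpoints, or about 90% to 96% with three. Give the basis alongside it: unadjusted t-test, SD of change 4.5, 80 patients evaluable at Week 12, position in the range depending on the other endpoints' results.
3. In 7.6, refer to 7.8 for the level at which PDSS is judged. The 0.05 there can be read as the familywise level, so nothing more is needed.
4. As useful detail, say in 7.4 whether 4.5 is the SD of the raw score or of the change, whether it is before or after baseline adjustment, and what missing data are assumed.

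The cost is one paragraph and one cross-reference, after a reconciliation that the SAP needs anyway. No patients are added and the choice of Hochberg can stay. The stated power becomes slightly less favourable.
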